7.1 Sponsor-Investigator Reporting Requirements

7.1.1 Reporting to the Human Research Protection Office (HRPO) at Washington University

Reporting will be conducted in accordance with Washington University IRB Policies.

Pre-approval of all protocol exceptions must be obtained prior to implementing the change.

7.1.2 Reporting to the Quality Assurance and Safety Monitoring Committee (QASMC) at Washington University

The Sponsor-Investigator is required to notify the QASMC of any unanticipated problems involving risks to participants or others occurring at WU or any BJH or SLCH institution that has been reported to and acknowledged by HRPO. (Unanticipated problems reported to HRPO and withdrawn during the review process need not be reported to QASMC.)

QASMC must be notified within **10 days** of receipt of IRB acknowledgment via email to [contact]. Submission to QASMC must include the myIRB form and any supporting documentation sent with the form.

7.1.3 Reporting to Pharmacyclics

All SAEs and AESIs (initial and follow-up information) will be reported on a MEDWATCH form 3500A or Suspect Adverse Event Report (CIOMS Form 1, IRB Reporting form) and sent via email ([contact]) or [contact] to Pharmacyclics Drug Safety, or designee, within 15 days of the event. Pharmacyclics may request follow-up and other additional information from the sponsor Investigator.

Pharmacyclics Inc.
[name]
[name]
[contact]
EMAIL: [contact]

Significant new information regarding an ongoing SAE and the resolution must be provided promptly to Pharmacyclics Inc. on the SAE form MEDWATCH 3500A.

7.1.3.1 Pregnancy

Before study enrollment, subjects must agree to take appropriate measures to avoid pregnancy of a sexual partner. However, should a pregnancy

occur in the partner of a study subject, consent to provide follow-up information regarding the outcome of the pregnancy and the health of the infant until 30 days old will be requested.

A subject must immediately inform the Investigator if his partner becomes pregnant from the time of consent to 90 days after the last dose of study drug. The Investigator should counsel the subject, discussing any risks of continuing the pregnancy and any possible effects on the fetus.

Although pregnancy itself is not regarded as an adverse event, the outcome will need to be documented. Any pregnancy occurring in a subject's partner from the time of first dose up until to 90 days after the last dose of study drug must be reported. Any occurrence of pregnancy must be reported to Pharmacyclics Drug Safety, or designee, per SAE reporting timelines of learning of the event. All pregnancies will be followed for outcome, which is defined as elective termination of the pregnancy, miscarriage, or delivery of the fetus. For pregnancies with an outcome of live birth, the newborn infant will be followed until 30 days old by completing the Pregnancy Report Form Part II and this must be reported to Pharmacyclics Drug Safety, or designee, per SAE reporting timelines. Any congenital anomaly/birth defect noted in the infant must be reported as a serious adverse event.

7.1.3.2 Other Malignancies

All new malignant tumors including solid tumors, skin malignancies and hematologic malignancies will be reported for the duration of study treatment and during any protocol-specified follow-up periods including post-progression follow-up for overall survival.

7.1.3.3 Adverse Events of Special Interest (AESI)

Specific adverse events, or groups of adverse events, will be followed as part of standard safety monitoring activities by the Sponsor. These events (regardless of seriousness) should be reported on the Serious Adverse Event Report Form and sent via email or fax to Pharmacyclics Drug Safety, or designee, within 15 days of awareness.

7.1.3.1.3 Major Hemorrhage

Major hemorrhage is defined as any of the following:

1. Any treatment-emergent hemorrhagic adverse events of Grade 3 or higher*.
2. Any treatment-emergent serious adverse events of bleeding of any grade
3. Any treatment-emergent central nervous system hemorrhage / hematoma of any grade

*All hemorrhagic events requiring transfusion of red blood cells should be reported as grade 3 or higher AE per CTCAE v4.03.

Events meeting the definition of major hemorrhage will be captured as an event of special interest according to Section 10.4.3 above.

7.1.4 Reporting to the FDA

The conduct of the study will comply with all FDA safety reporting requirements. **PLEASE NOTE THAT REPORTING REQUIREMENTS FOR THE FDA DIFFER FROM REPORTING REQUIREMENTS FOR HRPO/QASMC.** It is the responsibility of the Washington University principal investigator to report to the FDA as follows:

- Report any unexpected fatal or life-threatening suspected adverse reaction (refer to Appendix 5 for definitions) no later than **7 calendar days** after initial receipt of the information.
- Report a suspected adverse reaction that is both serious and unexpected (SUSAR, refer to Appendix 5) no later than **15 calendar days** it is determined that the information qualifies for reporting. Report an adverse event (refer to Appendix 5) as a suspected adverse reaction only if there is evidence to suggest a causal relationship between the drug and the adverse event, such as:
 - A single occurrence of an event that is uncommon and known to be strongly associated with drug exposure
 - One or more occurrences of an event that is not commonly associated with drug exposure but is otherwise uncommon in the population exposed to the drug
 - An aggregate analysis of specific events observed in a clinical trial that indicates those events occur more frequently in the drug treatment group than in a concurrent or historical control group
- Report any findings from epidemiological studies, pooled analysis of multiple studies, or clinical studies that suggest a significant risk in humans exposed to the drug no later than 15 calendar days after it is determined that the information qualifies for reporting.
- Report any findings from animal or in vitro testing that suggest significant risk in humans exposed to the drug no later than 15 calendar days after it is determined that the information qualifies for reporting.
- Report any clinically important increase in the rate of a serious suspected adverse reaction of that listed in the protocol or IB within 15 calendar days after it is determined that the information qualifies for reporting.

Submit each report as an IND safety report in a narrative format or on FDA Form 3500A or in an electronic format that FDA can process, review, and archive. Study teams must notify the Siteman Cancer Center Protocol Development team of each potentially reportable event within 1 business day after initial receipt of the information, and must bring the signed 1571 and FDA Form 3500A to the Siteman Cancer Center Protocol Development team no later than 1 business day prior to the due date for reporting to the FDA.

Each notification to FDA must bear prominent identification of its contents ("IND Safety Report") and must be transmitted to the review division in the Center for Drug Evaluation and Research (CDER) or in the Center for Biologics Evaluation and Research (CBER) that has responsibility for review of the IND. Relevant follow-up information to an IND safety report must be submitted as soon as the information is available and must be identified as such ("Follow-up IND Safety Report").

7.2 Exceptions to Expedited Reporting

Events that do not require expedited reporting as described in Section 7.1 include:

- planned hospitalizations
- hospitalizations < 24 hours
- respite care
- events related to disease progression

Events that do not require expedited reporting must still be captured in the EDC.

8 STUDY PROCEDURES AND OBSERVATIONS

8.1 Schedule of Procedures and Observations

The study-specific assessments are detailed in this section. Screening assessments must be performed within 28 days prior to the first dose of investigational product. Any results falling outside of the reference ranges may be repeated at the discretion of the investigator. All on-study visit procedures are allowed a window of +/- 3 days unless otherwise noted. Treatment or visit delays for public holidays or weather conditions do not constitute a protocol violation.

A written, signed, informed consent form (ICF) and a Health Insurance Portability and Accountability Act (HIPAA) authorization must be obtained before any study-specific assessments are initiated. A copy of the signed ICF will be given to the subject and a copy will be filed in the medical record. The original will be kept on file with the study records.

8.1.1 Pretreatment Period

8.1.1.1 Informed Consent

Before initiation of any screening procedures, each prospective subject will be provided a verbal, in-depth explanation of the study, requested to read the Institutional Review Board (IRB) approved informed consent form (ICF), and encouraged to ask questions. The Investigator must ensure that each subject understands how the study will be conducted and how they will participate if they so choose. The subject shall be given sufficient time to

properly consider the information and to make an informed decision regarding consent. Once all questions have been answered and the Investigator is assured that the subject understands the implications of study participation, the subject will be asked to provide written consent to participate in the study by signing the ICF. The Investigator will document the informed consent process in the subject's medical chart or progress notes and will provide a copy of the signed ICF to the subject.

8.1.1.2 Screening Assessments

The Screening procedures and assessments must be completed within 28 days of the first day of ibrutinib.

- Physical examination
- Vital signs
- Complete medical history
- Documentation of disease assessment
- ECOG Performance status
- Baseline concomitant medications taken within 28 days of Day 1
- Complete blood count (CBC) with differential and platelet count
- Blood chemistry assessment, including alkaline phosphatase, aspartate aminotransferase (AST), alanine aminotransferase (ALT), total bilirubin, calcium, phosphorus, blood urea nitrogen (BUN), creatinine, total protein, albumin, glucose, potassium, sodium, chloride, bicarbonate, lactate dehydrogenase (LDH)
- Coagulation assessment, including prothrombin time, partial thromboplastin time, international normalized ratio (PT/PTT/INR)
- PSA
- Hepatitis B surface antigen, anti-HBc antibody and anti-HBs antibody. In patients who have positive serology for the anti-HBc antibody, HBV DNA should be collected prior to Cycle 1, Day 1.
- HCV serology (anti-HCV antibody)
- HIV screening in accordance with national and/or institutional guidelines
- Serum collection in eight 10mL EDTA tubes for immune analyses to be sent to the TPC at Washington University
- Electrocardiogram (ECG)
- Pre-treatment tissue for correlative studies. If adequate tissue is available from a prior biopsy or surgery, samples will be requested from the hospital or clinic pathology department. If adequate tissue from a prior biopsy is not available, a prostate biopsy is required to participate in the study. There must be a minimum of 3 days between prostate biopsy and start of study drug.

8.1.2 Treatment Period

8.1.2.1 Study Procedures, Week 1, Day 1

- Physical examination
- Vital signs

- ECOG performance status
- Evaluation of adverse events
- Concomitant medications
- CBC with differential and platelet count
- Blood chemistry assessment, including alkaline phosphatase, AST, ALT, total bilirubin, calcium, phosphorus, BUN, creatinine, total protein, albumin, glucose, potassium, sodium, chloride, bicarbonate, LDH
- PSA

8.1.2.2 Study Procedures, Week 2, Day 8

- Telephone Visit
 - Evaluation of adverse events
 - Concomitant medications
 - Other pertinent interval history
- CBC with differential and platelet count (not required to be completed at Washington University, but results must be communicated to the CRC within protocol window)

8.1.2.3 Study Procedures, Week 3, Day 15

- Physical examination
- Vital signs
- ECOG performance status
- Evaluation of adverse events
- Concomitant medications
- CBC with differential and platelet count
- Blood chemistry assessment, including alkaline phosphatase, AST, ALT, total bilirubin, calcium, phosphorus, BUN, creatinine, total protein, albumin, glucose, potassium, sodium, chloride, bicarbonate, LDH

8.1.2.4 Study Procedures, Week 4, Day 22

- Telephone visit
 - Evaluation of adverse events
 - Concomitant medications
 - Other pertinent interval history
- CBC with differential and platelet count (not required to be completed at Washington University, but results must be communicated to the CRC within protocol window)

8.1.2.5 Study Procedures, Week 5, Day 29

- Physical examination
- Vital signs
- ECOG performance status
- Evaluation of adverse events

- Concomitant medications
- CBC with differential and platelet count
- Blood chemistry assessment, including alkaline phosphatase, AST, ALT, total bilirubin, calcium, phosphorus, BUN, creatinine, total protein, albumin, glucose, potassium, sodium, chloride, bicarbonate, LDH
- PSA
- Serum collection in eight 10mL EDTA tubes for immune monitoring to be sent to the TPC at Washington University

RP will be performed 7 to 12 days after the last dose of ibrutinib (between Week 6, Day 36 and Day 41).

8.1.3 Post-RP/Follow Up Visit (Week 10, Day 64):

Patients will be followed approximately 4 weeks after RP. The following procedures will be performed at the follow up Visit:

- Physical examination
- Vital signs
- ECOG performance status
- Evaluation of adverse events
- Concomitant medications
- CBC with differential and platelet count
- Blood chemistry assessment, including alkaline phosphatase, AST, ALT, total bilirubin, calcium, phosphorus, BUN, creatinine, total protein, albumin, glucose, potassium, sodium, chloride, bicarbonate, LDH
- PSA
- Serum collection in eight 10mL EDTA tubes for immune monitoring to be sent to the TPC at Washington University

8.1.4 Long Term Follow-up Procedures

The study will conclude when all enrolled patients have been followed 4 weeks after RP. All treatment related adverse events will be followed until resolution or stabilization to grade ≤ 2 .

8.1.5 Discontinuation of Therapy

The Investigator will withdraw a patient whenever continued participation is no longer in the patient's best interests. Reasons for withdrawing a patient include, but are not limited to, disease progression, the occurrence of an adverse event or a concurrent illness, a patient's request to end participation, a patient's non-compliance or simply significant uncertainty on the part of the investigator that continued participation is prudent. There may also be administrative reasons to terminate participation, such as concern about a patient's compliance with the prescribed treatment regimen.

8.2 Schedule of Study Procedures and Assessments

Study Day/Visit Day	Screening D-28 to 0 +/- 3 days	Week 1 D1 +/- 3 days	Week 2 D8 +/- 3 days	Week 3 D15 +/- 3 days	Week 4 D22 +/- 3 days	Week 5 D29 +/- 3 days	RP D36 to D41 ⁷	Post-RP Follow Up Visit +/- 3 days ⁸
Informed consent	X							
AE assessment		X	X ⁶	X	X ⁶	X		X
Concomitant medications	X	X	X ⁶	X	X ⁶	X		X
Pre-treatment prostate biopsy tissue available	X							
Treatment/Drug Administration								
Ibrutinib			Oral daily, D1 to D28					
Clinical procedures								
Telephone visit			X ⁶		X ⁶			
Physical exam	X	X		X		X		X
Vital signs	X	X		X		X		X
Medical history	X							
Disease assessment	X ⁹							
ECOG performance status	X	X		X		X		X
Laboratory procedures								
CBC with differential	X	X	X ⁶	X	X ⁶	X		X
Blood chemistry + LDH ¹	X	X		X		X		X
Glucose	X	X		X		X		X
Coagulation ²	X							
PSA	X	X				X		X
Hepatitis B and C ³	X							
HIV ⁴	X							
Immune monitoring ⁵	X					X		X
Urinalysis	X							
Imaging procedures								
ECG	X							

Radical Prostatectomy

1. Blood chemistry assessment includes alkaline phosphatase, AST, ALT, total bilirubin, calcium, phosphorus, BUN, creatinine, total protein, albumin, potassium, sodium, chloride, bicarbonate, and LDH.

2. Coagulation assessment includes PT, PTT and INR.

3. Serum hepatitis assessment includes HBsAg, HBsAb, HBcAb, and anti-HCV antibody.

4. HIV screening with ELISA based assay.

5. Refer to Appendix 3.

6. Obtained during telephone visits; CBC may be done at a local lab.

7. 7-12 days after the last dose of ibrutinib

8. Week 10, Day 64

9. Window for disease assessment is up to 60 days prior to enrollment

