3.3 Eligibility Criteria

Patients must have baseline evaluations performed prior to the first dose of study drug and must meet all inclusion and exclusion criteria. In addition, the patient must be thoroughly informed about all aspects of the study, including the study visit schedule and required evaluations and all regulatory requirements for informed consent. The written informed consent must be obtained from the patient prior to enrollment. The following criteria apply to all patients enrolled onto the study unless otherwise specified.

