6 TREATMENT PLAN

6.1 Dosage and Administration

Ibrutinib is administered orally once daily on an outpatient basis at a dose of 840 mg. The capsules are to be taken around the same time each day with 8 ounces (approximately 240 mL) of water, with or without food. The capsules should be swallowed intact and subjects should not attempt to open capsules or dissolve them in water. The use of strong CYP3A inhibitors/inducers, and grapefruit and Seville oranges should be avoided for the duration of the study. Examples of inhibitors, inducers, and substrates can be found at <http://medicine.iupui.edu/clinpharm/ddis/main-table/>

If a dose is not taken at the scheduled time, it can be taken as soon as possible on the same day with a return to the normal schedule the following day. The subject should not take extra capsules to make up the missed dose.

The first dose will be delivered in the clinic on Day 1, after which subsequent dosing is typically on an outpatient basis. Ibrutinib will be dispensed to subjects in bottles at each visit. Study drug may not be shipped to the subject without approval from PCYC and may not be dispensed to anyone other than the subject. Unused ibrutinib dispensed during previous visits must be returned to the site and drug accountability records updated at each visit. Returned capsules must not be re-dispensed to anyone.

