12.6.3 Analysis of Secondary Endpoints

12.6.3.1 Circulating immune subsets

For each patient, flow cytometry of circulating immune cell subsets will also be performed on pre-treatment blood and again after RP. Established flow

cytometry panels will examine B cell and T cell populations. Immune cell quantification will be summarized by changes from baseline to after treatment using descriptive statistics. Furthermore, paired Wilcox on signed-rank test will be applied to test the pre-post treatment changes. When available, immune cells digested from resected tumor tissues will also be assessed by flow cytometry.

12.6.3.2 Cytotoxic effects and clinical benefits: rate of downstaging, pT0 rate, $\geq 50\%$ PSA decline (phase II)

Point estimates and 95% confidence intervals of pathologic T0 rate at the time of RP will be obtained for phase 2 subjects treated with ibrutinib. Pathologic T0 rate at the time of RP will be compared with the null hypothesis rate separately by using binomial test.

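### The only pre-drug immune blood is drawn at screening, up to 28 days before the first dose, although Day 1 already has a clinic blood draw; the screening header in the 8.2 table also conflicts with the text

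*Combined protocol and SAP*

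**What the plan says.** **The endpoint.** Section 2.2.2 classifies each man by whether a circulating subset falls at least 2-fold from pre-treatment to post-treatment. Section 12.6.3.1 adds a paired Wilcoxon signed-rank test and fixes the samples: "flow cytometry of circulating immune cell subsets will also be performed on pre-treatment blood and again after RP".

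**The pre-drug sample.** Section 8.1.1.2 lists under screening: "Serum collection in eight 10mL EDTA tubes for immune analyses to be sent to the TPC at Washington University". The immune-monitoring row of the 8.2 table is marked at Screening, Week 5 and the post-RP visit only. The Research Blood Form in Section 11 and Appendix 3 agree on three time points.

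**Day 1.** Section 6.1 states: "The first dose will be delivered in the clinic on Day 1". Section 8.1.2.1 lists CBC, chemistry and PSA for that visit, with no immune tubes. PSA is collected both at baseline and at Week 1.

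**The window.** Section 3.3: "Patients must have baseline evaluations performed prior to the first dose of study drug". Section 8.1: "Screening assessments must be performed within 28 days prior to the first dose of investigational product". Section 8.1.1.2: "The Screening procedures and assessments must be completed within 28 days of the first day of ibrutinib". Section 8.1 gives the tolerance to a different class of visit: "All on-study visit procedures are allowed a window of +/- 3 days unless otherwise noted". The 8.2 table nevertheless heads its first column "Screening D-28 to 0 +/- 3 days".

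**The concern.** A paired before-and-after test reads the change as the effect of the drug. Any time between the baseline draw and the first dose adds ordinary within-man fluctuation to that change, and can add an event unrelated to ibrutinib, such as a treated infection. The 2-fold classification is exposed in the same way: an unrepresentative baseline can move a man across the threshold. The circulating-cell analysis has no control group to show how much of the change is background, because the reference cohort in Section 12.7 supplies prostatectomy tissue. The gap is avoidable, since the man is in the clinic having blood drawn on the day of his first dose.

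The table header is a second, separate matter. Its tolerance extends the column past the 28-day limit at one end and past the first dose at the other, so staff working from the table and staff working from the text would apply different windows.

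**Working it through.** **Step 1. How many pre-drug immune samples are there?** Sections 8.1.1.2, 8.1.2.1, 8.2, 11 and Appendix 3, taken together, give three immune draws: screening, Week 5 (Day 29) and the post-RP visit (Day 64). Only screening precedes the drug.

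**Step 2. How much off-drug time does the baseline allow?** Let b be the number of days from the baseline draw to the first dose on Day 1. The interval to a sample on Day d is b + (d - 1), and the pre-dose share is b divided by that interval.

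| Baseline draw | b | To Day 29 | Pre-dose share | To Day 64 | Pre-dose share |
|---|---|---|---|---|---|
| Earliest under the 8.1 text | 28 | 28 + 28 = 56 days | 28/56 = 50% | 28 + 63 = 91 days | 28/91 = 31% |
| Day -28 on the table's count, with a Day 0 | 29 | 57 days | 29/57 = 51% | 92 days | 29/92 = 32% |
| Day 1, pre-dose | 0 | 28 days | 0% | 63 days | 0% |

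The Day 64 columns describe the comparison that Section 12.6.3.1 names. The Day 29 columns apply if the end-of-treatment sample is used for the post-treatment change in Section 2.2.2. These are maxima; a man screened a few days before Day 1 has a short gap.

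**Step 3. What does the header allow if taken literally?** The early end is -28 - 3 = Day -31, which is 32 days before Day 1 if a Day 0 exists and 31 if not. The late end is 0 + 3 = Day 3. With daily dosing from Day 1, a Day 3 draw follows two doses if taken before that day's dose and three if taken after it. Against this, Section 8.1 allows at most 28 days before the first dose, and Section 3.3 requires baseline before the first dose. The header conflicts with the text at both ends.

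**Step 4. Would the Day 1 column solve the problem as printed?** Not without an instruction. It also carries a 3-day tolerance, which reaches 1 + 3 = Day 4, and Section 8.1.2.1 does not say that the Day 1 bloods precede the dose.

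**Step 5. Can the loss be sized?** With equal variances, the variance of a paired difference is 2 x sigma^2 x (1 - rho), where rho is the correlation between the two samples in the same man. A longer gap costs precision only as far as it lowers rho. The documents give neither sigma nor rho for any circulating subset, and no power statement for this endpoint, so the size cannot be computed.

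**The case against.** The strongest reply is that a screening-window baseline is a design choice for an unpowered secondary endpoint that is also summarised descriptively. Under the governing text it adds noise rather than a demonstrated bias. Moving the draw shortens the interval to the Day 64 sample only from 91 to 63 days at most, and what remains still spans surgery and about five weeks off drug (Day 28 to Day 64 is 36 days). These are larger non-drug influences than the screening gap. All of this stands and limits the gain.

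The eligibility criteria also control some intercurrent events: steroids within 28 days of screening, immunosuppressive therapy within 21 days of first dose, live vaccines within 4 weeks of first dose, and infections whose systemic treatment ended within 14 days before the first dose. The protection is partial. A man sampled near Day -28 during an infection whose treatment ends before that 14-day period remains eligible, with that sample as his baseline.

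A repeat biopsy is a weaker argument for moving the draw. It applies only when archival tissue is unavailable or inadequate, and because only 3 days are required between biopsy and drug, a Day 1 draw could fall soon after it.

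A reader might infer from the header that the plan permits a baseline taken after two or three doses, and might link this to the early lymphocyte rise in Section 1.2.1.3. The documents do not support that. Sections 3.3 and 8.1 put baseline before the first dose, Section 4 bars any protocol intervention before eligibility is confirmed and the patient registered, and Section 12.6.3.1 calls the sample pre-treatment. The same column holds consent and the eligibility blood tests, which cannot run to Day 3. The rise in Section 1.2.1.3 was seen in preclinical models and CLL patients.

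**Conclusion.** The point holds as an avoidable weakness of minor to moderate size, confined to a secondary endpoint. The baseline for circulating cells may precede the first dose by up to 28 days. That is up to 31% of the interval to the Day 64 sample, or 50% of the interval to Day 29, when a same-day draw was available. It does not invalidate the signed-rank test or the 2-fold classification; it makes both less precise than they need be. The day counts rest on the nominal visit days and on draws at the earliest permitted time.

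A reader might want to express the loss as an equivalent number of men. That needs assumed correlations. If rho is 0.80 at the shorter interval and anywhere from 0.80 down to 0.70 at the longer one, the variance ratio (1 - rho long)/(1 - rho short) runs from 0.20/0.20 = 1.0, no loss, to 0.30/0.20 = 1.5. The answer is whatever is assumed, so it should not be reported as a finding.

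The 8.2 header contradicts Sections 3.3 and 8.1 and must be reconciled with them. It is an inconsistency in the table and does not show that post-dose baselines are allowed.

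**What to change.** 1. In Sections 8.1.1.2 and 8.1.2.1, the 8.2 table and the Research Blood Form schedule in Section 11, move the baseline immune tubes from screening to Day 1, explicitly before the first dose.
2. In the 8.2 table, remove the plus-or-minus 3 days from the screening column so that it matches Section 8.1.
3. In Section 8.1.2.1 and the Day 1 column, state that the blood draws precede the first dose, so that the on-study tolerance cannot carry them past it.
4. In Section 12.6.3.1, name the Day 1 pre-dose sample as the pre-treatment blood.

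The cost is a set of text and table edits, with no added visit or tube. Men who fail screening are spared a research draw of 8 x 10 = 80 mL. The downside is that sample processing must be available on Day 1, and a failed Day 1 sample cannot be repeated once dosing has begun. The Tissue Procurement Core already handles the same tubes at Week 5 and after surgery, so this is a matter of scheduling.
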